6.4 Derived Variables

Duration of Rheumatoid Arthritis

The number of years between the date of diagnosis (DXDT) and Run-in Day 1, rounded to one decimal place, is given by formula below to calculate the duration:

Observed portion	Missing portion	Formula to Calculate Duration
Year, Month, Day		$(\text{Run-in Day 1} - \text{DXDT} + 1)/365.25$
Year, Month	Day	$[\text{Year}(\text{Run-in Day 1}) - \text{Year}(\text{DXDT})] + [\text{Month}(\text{Run-in Day 1}) - \text{Month}(\text{DXDT})]/12$ *if duration equals 0, add 1 month or 1/12 years (to avoid a disease duration of 0)
Year	Month, Day	$[\text{Year}(\text{Run-in Day 1}) - \text{Year}(\text{DXDT})]$ *if duration equals 0, add 1 month or 1/12 years (to avoid a disease duration of 0)

Time to Disease-Worsening

Time to Disease-Worsening = DW Date – Study Day 1 + 1

The subjects without Disease-Worsening will be censored at their last SDAI assessment date.

Only time to subject's *first* instance of disease-worsening will be evaluated.

Time-to-Event (for Rescue Analysis Set)

Time-to-Event = Earliest Date of Achievement of Event of Interest During the Rescue Therapy Period – Rescue Date + 1

For example, for subjects who recapture SDAI remission:

Time-to-Recapture SDAI remission = Earliest Date of Achievement of Observed SDAI remission During the Rescue Therapy Period – Rescue Date + 1

The subjects who do not experience the event of interest will be censored at their last SDAI assessment date.

Only time to subject's *first* instance of each event of interest will be evaluated.

Time-to-Event (for Disease-Worsening Analysis Set)

Time-to-Event = Earliest Date of Achievement of Event of Interest After
Disease-Worsening – DW Date + 1

For example, for subjects who recapture SDAI remission:

Time-to-Recapture SDAI remission = Earliest Date of Achievement of Observed SDAI
remission After Disease-Worsening – DW Date + 1

The subjects who do not experience the event of interest will be censored at their last SDAI assessment date.

Only time to subject's *first* instance of each event of interest will be evaluated.

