### **6.2.1.1 Dosage, Administration, and Schedule**

Etanercept dosing in the study will follow the recommended label dosing for subjects with RA (subcutaneous injection, 50 mg once weekly). Etanercept will be provided as a 50-mg PFS (0.98 mL of a 50- mg/mL solution of etanercept). Each dose of investigational product will consist of the complete contents of 1 syringe. The injection site should be rotated with each dose. During the open-label run-in period subjects will receive 1 dose of etanercept per week (scheduled approximately 7 days apart) for 24 weeks. During the double-blind treatment period, subjects will receive 1 dose of etanercept or matching placebo per week (scheduled approximately 7 days apart) for 48 weeks. Throughout the entire trial, administration of etanercept should occur on the scheduled dose day; however, if unavoidable, it may be given earlier or later as long as the dose is not within 2 days of the next scheduled dose. If the dosing window is missed, that dose should be skipped and the reason for the missed dose must be reported on the case report form. Subsequent doses of investigational product should resume on the original schedule, calculated from the run-in visit 1 for the open label run-in period of the study and from Day 1 for the double-blind treatment period. If etanercept is to be taken the day of a study visit, it must be taken after the study visit has occurred (ie, at the subject's location on the scheduled dose day). Injections of etanercept will be administered by the subject or a caregiver. The individual administering the dose must demonstrate to the site staff that he or she is competent to correctly administer the subcutaneous doses. The first dose of etanercept in the open label run-in period and Day 1 in the double-blind treatment period must be administered at the study site. All subsequent doses will be administered at the subject's location on the scheduled dose day. Supplies of etanercept will be dispensed to subjects for administration at home. The site will instruct the subject in appropriate handling and storage of used and unused syringes and documentation of dosing in the subject diary. The dose date, quantity administered and box number of investigational product are to be recorded in each subject's diary/ electronic case report form (eCRF). Please refer to the Investigator's Brochure for the most recent safety information. A link to the United States Prescribing Information can be found in the Investigator's Brochure.

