### **7.2.6 Treatment**

Visits will occur per the Schedule of Assessments ([Table 1](#)) during the treatment period from day 1 until week 48. On-study visits may be completed within  $\pm 7$  days of the target visit date. The procedures completed during the 48-week treatment period are those listed in the Schedule of Assessments ([Table 1](#)). Administration of investigational product is to be administered after all other study procedures, as applicable, during each visit that is required.

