#### **7.3.8.3 Simplified Disease Activity Index (SDAI)**

The SDAI is the numerical sum of five outcome parameters: tender joint count and swollen joint count based on a 28-joint assessment, patient global assessment of disease activity, physician global assessment of disease activity and C-reactive protein (CRP in mg/dL). SDAI is calculated by the sponsor.

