Disease-Worsening Date (DW Date)

A subject's Disease-Worsening Date is the first Visit Date in which the subject meets the definition for Disease-Worsening. With the exception of analysis using multiple imputation method, Disease-Worsening classification is based on observed SDAI values only. Each subject will have at most one DW Date. A subject's disease-worsening date is used to define his/her Disease-Worsening Baseline.

Rescue Date

A subject's rescue date is the Visit Date in which he or she first receives rescue therapy as identified by the Investigational Product Administration (Rescue Therapy Etanercept) or Investigational Product Administration (Rescue Therapy Methotrexate) form.

Rescue Therapy Period

For the Rescue Analysis Set as defined in [Section 7.4](#), the Rescue Therapy Period begins with the Rescue Date through the EOS Date.

Disease-Worsening Analysis Visit (DW_visit)

The DW_visit defines the analysis visit after a subject fulfills disease-worsening criteria. Details of DW_visit derivation are in [Appendix A](#).

Rescue Analysis Visit (Rescue_visit)

Rescue_visits define the analysis visits after a subject initiates rescue therapy. Details of Rescue_Visit derivation are in [Appendix A](#).

End of Treatment (EOT)

The End of Treatment for a subject is the subject's last assessment for the protocol-specified treatment phase of the study.

End of Study Date

The End of Study Date for a subject is the date the subject completes the safety follow-up phone call, or the date of the Early Termination (ET) visit if no safety follow-up phone call is completed. The date the subject has ended the study is recorded on the End of Study Electronic Case Report Form (eCRF).

End of Study

The End of Study is the date when the last subject across all sites is assessed or receives an intervention for evaluation in the study (ie, last subject last visit).

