“Rescue Baseline” is defined as the latest assessment on or before a subject’s rescue date.

Let $Visit_0$ = the Analysis Visit at which a subject initiates rescue, where Analysis Visit is for SDAI score and is defined in the Double-Blind Treatment Period Analysis Visits Table above.

Let $Visit_1$ represent the Analysis Visit on or after $Visit_0$.

Then $Rescue_visit$ will be defined as follows:

If subject has received rescue (Study Day Subject Received Rescue \leq Study Day):

- $Rescue_visit = 12$,
If $Visit_1 - Visit_0 = 0$ or 12
- $Rescue_visit = Visit_1 - Visit_0$,
Otherwise.

If a subject has not yet received rescue at a specific visit, $Rescue_visit$ missing.

If a subject has multiple observations for the same $Rescue_Visit$, the latest observation will be used in the analysis.

Efficacy Endpoint Scoring Algorithms

Abbreviations:

TEN28	28-joint Tender Joint Count
SW28	28-Joint Swollen Joint Count
PtGA	Patient Global Assessment
PhGA	Physician Global Assessment
ESR	Erythrocyte Sedimentation Rate

Simplified Disease Activity Index (SDAI)

The SDAI is a composite measure that sums the total number of tender and swollen 28-joint counts, the PtGA on a 0-10 scale, the PhGA on a 0-10 scale, and the CRP in mg/dL. PtGA and PhGA are collected in a 0-100 scale, so they will need to be divided by 10.

The SDAI is scored as follows:

$$\text{TEN28} + \text{SW28} + \text{PtGA}/10 + \text{PhGA}/10 + \text{CRP (mg/dL)}$$

Clinical Disease Activity Index (CDAI)

The CDAI is a further simplification of the SDAI that excludes the acute phase reactant. It sums the total number of tender and swollen 28-joint counts, the PtGA on a 0-10 scale and the PhGA on a 0-10 scale. PtGA and PhGA are collected in a 0-100 scale, so they will need to be divided by 10.

The CDAI is calculated using the following formula:

$$\text{TEN28} + \text{SW28} + \text{PtGA}/10 + \text{PhGA}/10$$

DAS28-CRP

A subject's DAS28-CRP score is calculated as follows:

$$\text{DAS28-CRP} = 0.56*\sqrt{\text{TEN28}} + 0.28*\sqrt{\text{SJC28}} + 0.36*\ln(\text{CRP}+1) + 0.014*\text{PtGA} + 0.96,$$

where CRP is measured in mg/L.

DAS28-ESR

A subject's DAS28-ESR score is calculated as follows:

$$\text{DAS28-ESR} = 0.56*\sqrt{\text{TEN28}} + 0.28*\sqrt{\text{SJC28}} + 0.70*\ln(\text{ESR}) + 0.014*\text{PtGA},$$

where ESR is measured in mm/hr.

Swollen Joint Count

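### For the Rescue Analysis Set, an SDAI taken on the Rescue Date, before the first rescue dose, can count as an event on day 1

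*SAP*

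**What the plan says.** SAP 6.4 defines time to event in the Rescue Analysis Set as event date minus Rescue Date plus 1. For recapture of remission, the event date is the "Earliest Date of Achievement of Observed SDAI remission During the Rescue Therapy Period". SAP 6.1 sets the window: "the Rescue Therapy Period begins with the Rescue Date through the EOS Date". It also says that a subject's "rescue date is the Visit Date in which he or she first receives rescue therapy", so the start day is a visit day and lies inside the window. The same formula serves every event of interest in this set, including time to SDAI low disease activity (LDA) and time to DAS28 remission.

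The order of events within a visit is in the protocol. Section 7.2.6 says "Administration of investigational product is to be administered after all other study procedures". Section 6.2.1.1 adds "If etanercept is to be taken the day of a study visit, it must be taken after the study visit has occurred". Section 7.4 has blood, and so CRP, drawn before product is given. No separate dosing order is stated for the first rescue dose.

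In SAP Appendix A, under Time After Rescue, Rescue Baseline "is defined as the latest assessment on or before a subject"'s rescue date.

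**The concern.** The rescue-day assessment precedes the treatment whose effect the endpoint is meant to describe, yet the formula admits it as an event. Two other places in the plan use a different boundary. The parallel formula for the Disease-Worsening Analysis Set in SAP 6.4 counts only events after worsening. The endpoint in Protocol 10.1.1.2 is recapture once rescue treatment has started. The Rescue Analysis Set formula departs from both.

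Remission and time to its recapture after rescue form a stated secondary objective, analysed with Kaplan-Meier curves and log-rank tests. An event that belongs at a later visit, or a subject who should be censored, would appear as an immediate success of rescue.

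**Working it through.** The documents give no figure for this endpoint, so there is none to reproduce. The check applies the definitions to dates and then asks when the result goes wrong.

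**1. The date formula.**
- Remission recorded on the Rescue Date: (Rescue Date − Rescue Date) + 1 = 1 day.
- The same subject, if first counted at a visit 84 days later (12 weeks, the scheduled interval in Protocol Table 1): 84 + 1 = 85 days.
- Neither document excludes the first result.

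**2. When a rescue-day remission can occur.** All three worsening criteria (SAP 6.5) need SDAI > 3.3 at the qualifying visit. If rescue starts at that visit, a day-1 remission is impossible. Three things are needed together: a Rescue Date later than the Disease-Worsening Date, a complete SDAI on the Rescue Date, and a value ≤ 3.3.

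**3. Whether the documents allow this.** Protocol 7.3.8.3 says "SDAI is calculated by the sponsor", and Protocol 7.4 sends CRP to the central laboratory, so the score may not be known during the visit. SAP 6.1 defines the two dates separately. The Disease Assessment column of Protocol Table 1 holds every SDAI component and also rescue dispensing. No turnaround time or share of delayed starts is given.

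**4. Possible number of day-1 remissions (assumed inputs).** Under the planning rates of 50% and 72% with 100 subjects per arm, at most 100 × (1 − 0.50) = 50 methotrexate and 100 × (1 − 0.72) = 28 etanercept subjects are rescued. These are ceilings, because non-responders include dropouts.
- No delayed starts: 0.
- Half start later and 10% of those are at ≤ 3.3: 0.5 × 0.10 = 5%; 0.05 × 50 = 2.5 methotrexate subjects.
- Half start later and 25% of those are at ≤ 3.3: 0.5 × 0.25 = 12.5%; 0.125 × 50 = 6.25 methotrexate subjects.

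**5. The median (assumed 35% recapture per 12-week visit).**
- Without day-1 events, the share not yet recaptured is 0.65 after one visit and 0.65² = 0.42 after two, so the median falls at the second visit.
- With 12.5% day-1 events it is 0.875 × 0.65 = 0.57, then 0.875 × 0.42 = 0.37. The median is still at the second visit.
- To move it to the first visit, (1 − s) × 0.65 must reach 0.50, so s = 1 − 0.50/0.65 = 23%. A per-visit rate just below 50% would need a smaller share.

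**6. The log-rank test.** Simulation with 50 and 28 rescued subjects, 35% recapture per visit, 1 to 3 visits left, no true difference after rescue, and 3,000 runs per scenario:

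| Share with rescue-day SDAI ≤ 3.3, methotrexate / etanercept | Rejection at nominal 5% |
|---|---|
| 0 / 0 | 5.5% |
| 5% / 5% | 5.0% |
| 10% / 10% | 5.4% |
| 0 / 10% | 12.2% |
| 5% / 15% | 10.7% |
| 5% / 20% | 18.7% |
| 10% / 25% | 19.7% |
| 10% / 25%, rescue-day values not counted | 5.4% |

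Only an unequal share distorts the test, and the documents give no share for either arm.

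**7. LDA.** SAP 6.5 defines SDAI LDA as 3.3 < SDAI ≤ 11. The first two worsening criteria are met by an SDAI in exactly that range. A subject rescued at that visit is already in LDA, so the time is 1 day by definition. A subject rescued that day with SDAI > 11 is not affected.

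**The case against.** The strongest reply is that the recapture problem may never occur. Protocol 3.1.2 and Table 1 footnote f describe re-dispensing once the criteria are met, which can be read as the same visit. Protocol 7.2.7 gives two purposes for a Disease Assessment visit: run-in eligibility, and deciding whether rescue can be given. A visit made only to collect product is neither, so a full SDAI there is not assured. SAP 12 explains the separate disease-worsening set by subjects who worsen but never receive rescue, not by delay. The Rescue Date is read from product administration forms, and most doses are taken at home; a home-dose date would carry no SDAI.

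Most of this stands as a limit on reach. It does not remove the rule. A start at the next scheduled visit, which has a full SDAI, remains possible. The home-dose argument would also spare the LDA endpoint, but SAP 6.1 calls the Rescue Date a visit date.

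A reader might infer that reported recapture is generally inflated, that the median is shortened, that the comparison between arms is biased, or that spontaneous remission is credited to rescue. The documents support none of these. They give no frequency, and the median and log-rank effects appear only under particular assumptions. A value back at ≤ 3.3 could also reflect measurement fluctuation or the short corticosteroid course that Protocol 6.5.2 permits. A reader might also want to drop subjects already at ≤ 3.3 at Rescue Baseline. Protocol 10.1.1.2 defines the population as subjects who receive rescue, so that would change the endpoint's population.

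**Conclusion.** The rule is wrong as written: it admits a pre-dose value as an outcome of rescue and lets one record be both baseline and event. That the value is pre-dose rests on the protocol's general procedure order.

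For the secondary endpoint, time to recapture SDAI remission, the error is conditional and of unknown size. Under the assumptions shown it runs from 0 to about 6 methotrexate subjects. For the exploratory time to SDAI LDA, it affects every subject rescued at the qualifying visit with SDAI > 3.3 and ≤ 11, with no delay needed. The secondary tests carry no multiplicity adjustment (SAP 11.1). The primary endpoint is unaffected.

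**What to change.** In SAP 6.4, count events for the Rescue Analysis Set only from assessments dated after the Rescue Date. Use a rescue-day value only as Rescue Baseline, and apply the same boundary to the rescue-visit rule in Appendix A, which also admits the rescue-day record. Report by arm how many subjects already met each event at Rescue Baseline. For LDA this count is needed in any case, because a subject who simply stays in that range would still become an event at the next visit.

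Keep the Rescue Analysis Set as the main population. Restriction to Rescue Baseline SDAI > 3.3 should be a sensitivity analysis at most.

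The cost is one inequality and one extra count, with no new data. The downside is that recapture times become slightly less favourable.

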6.5 Study Endpoints

Patient Global Assessment of Joint Pain (PtGAJP)

An assessment of the severity of the subject's joint pain (0=no pain at all, 100=worst pain imaginable) completed by the patient using a visual analog scale (VAS) in mm.

Patient Global Assessment of Disease Activity (PtGA)

A global assessment of the subject's arthritis (0=no arthritis activity at all, 100=worst arthritis activity imaginable) completed by the patient using a visual analog scale (VAS).

Physician Global Assessment of Disease Activity (PhGA)

A global assessment of the subject's arthritis (0=no activity at all, 100=worst activity imaginable) completed by the physician using a visual analog scale (VAS).

Swollen Joint Count

A score that assesses the presence or absence of swelling in 66 joints. There are also a 28-joint Swollen Joint Count and a 28-joint Plus Feet and Ankles Swollen Joint Count. Details of the scoring algorithm are described in [Appendix A](#).

Tender Joint Count

A score that assesses the presence or absence of tenderness in 68 joints. There are also a 28-joint Tender Joint Count and a 28-joint Plus Feet and Ankles Tender Joint Count. Details of the scoring algorithm are described in [Appendix A](#).

Simplified Disease Activity Index (SDAI)

A composite score that is based on the number of tender and swollen joints using a 28-joint count, PhGA (0-10 visual analog scale), PtGA (0-10 visual analog scale), and CRP in mg/dL. A higher score represents worse disease.

Details of the scoring algorithm are described in [Appendix A](#).

SDAI Remission at Analysis Visit k

For Analysis Visits other than Week 48, SDAI Remission at a given Visit will be derived using the same approach as in [Section 6.2](#), replacing Week 48 with the Analysis Visit Week k , and replacing “subject did not fulfill the definition of disease-worsening during the study” with “subject did not *previously* fulfill the definition of disease-worsening”.

Specifically,

- SDAI_remission_maintenance (≤ 3.3) at Week $k = 1$,
if SDAI ≤ 3.3 at Week k AND subject did not previously fulfill the definition of disease-worsening;
- SDAI_remission_maintenance (≤ 3.3) at Week $k = \text{missing}$,
if subject has no Week k SDAI value AND subject did not previously fulfill the definition of disease-worsening;
- SDAI_remission_maintenance (≤ 3.3) at Week $k = 0$,
otherwise.

Observed SDAI Remission at Analysis Visit k

- Observed_SDAI_Remission at Analysis Visit $k = 1$,
if SDAI ≤ 3.3 at Analysis Visit k ;
- Observed_SDAI_remission (≤ 3.3) at Analysis Visit $k = \text{missing}$,
if subject has no SDAI value at Analysis Visit k ;
- Observed_SDAI_remission (≤ 3.3) at Analysis Visit $k = 0$,
if SDAI > 3.3 at Analysis Visit k .

Observed SDAI Remission at DW Visit (or Rescue Visit) k

- Observed_SDAI_Remission at DW Visit (or Rescue Visit) $k = 1$,
if SDAI ≤ 3.3 at DW Visit k ;
- Observed_SDAI_remission (≤ 3.3) at DW Visit (or Rescue Visit) $k = \text{missing}$,
if subject has no SDAI value at DW Visit k ;
- Observed_SDAI_remission (≤ 3.3) at DW Visit (or Rescue Visit) $k = 0$,
if SDAI > 3.3 at DW Visit k .

Disease Activity

For a specific timepoint, subjects are classified as having

- SDAI Low Disease Activity (LDA): $3.3 < \text{SDAI} \leq 11$
- SDAI Moderate Disease Activity (MDA): $11 < \text{SDAI} \leq 26$
- SDAI High Disease Activity (HDA): $\text{SDAI} > 26$

Disease-Worsening

During the double-blind treatment period, disease-worsening for the study is defined as:

- $\text{SDAI} > 3.3$ and ≤ 11 on two consecutive visits at least two weeks apart OR
- $\text{SDAI} > 3.3$ and ≤ 11 on three or more separate visits OR
- $\text{SDAI} > 11$ at anytime

Disease-Worsening may be assessed at a regularly scheduled visit or at an unscheduled Disease Assessment visit. Subjects will remain on study and complete all study visits.

Disease Activity Score using the erythrocyte sedimentation rate formula (DAS28-ESR)

A modified composite index that was designed to measure disease activity in subjects using the number of tender and swollen joints based upon a 28-joint count, ESR in mm/hr, and a 100 mm visual analog scale measuring the subject's general health. A higher score represents worse disease.

Details of the scoring algorithm are described in [Appendix A](#).

Disease Activity Score using the C-reactive protein formula (DAS28-CRP)

A composite index that was designed to measure disease activity in subjects using the number of tender and swollen joints based upon a 28-joint count, CRP in mg/L, and a 100 mm visual analog scale measuring the subject's general health. A higher score represents worse disease.

Details of the scoring algorithm are described in [Appendix A](#).

DAS28-ESR remission

Subjects are classified as achieving DAS28-ESR remission at a specific timepoint if their DAS28-ESR < 2.6 at that timepoint. Specifically, let DAS28ESR_remission be defined as follows:

- DAS28ESR_remission (< 2.6) = 1, if DAS28-ESR < 2.6;
- DAS28ESR_remission (< 2.6) = missing, if subject has no DAS28-ESR value;
- DAS28ESR_remission (<2.6) = 0, otherwise.

DAS28-ESR LDA

Subjects are classified as achieving DAS28-ESR LDA at a specific timepoint if their DAS28-ESR \geq 2.6 and < 3.2 at that timepoint. Specifically, let DAS28ESR_LDA be defined as follows:

- DAS28ESR_LDA = 1, if DAS28-ESR \geq 2.6 and < 3.2;
- DAS28ESR_LDA = missing, if subject has no DAS28-ESR value;
- DAS28ESR_LDA = 0, otherwise.

DAS28-CRP remission

Subjects are classified as achieving DAS28-CRP remission at a specific timepoint if their DAS28-CRP < 2.6 at that timepoint. Specifically, let DAS28CRP_remission be defined as follows:

- DAS28CRP_remission (< 2.6) = 1, if DAS28-CRP < 2.6;
- DAS28CRP_remission (< 2.6) = missing, if subject has no DAS28-CRP value;
- DAS28CRP_remission (<2.6) = 0, otherwise.

DAS28-CRP LDA

Subjects are classified as achieving DAS28-CRP LDA at a specific timepoint if their DAS28-CRP ≥ 2.6 and < 3.2 at that timepoint. Specifically, let DAS28CRP_LDA be defined as follows:

- DAS28CRP_LDA = 1,
if DAS28-CRP ≥ 2.6 and < 3.2 ;
- DAS28CRP_LDA = missing,
if subject has no DAS28-CRP value;
- DAS28CRP_LDA = 0,
otherwise.

Clinical Disease Activity Index (CDAI)

A composite score that is based on the number of tender and swollen joints using a 28-joint count, PhGA (0-10 visual analog scale), and PtGA (0-10 visual analog scale). A higher score represents worse disease.

Details of the scoring algorithm are described in [Appendix A](#).

Boolean remission status (28-joint count)

A subject achieves Boolean remission (28-joint count) if all of the following criteria are met:

- 28-joint tender joint count ≤ 1 ,
- 28-joint swollen joint count ≤ 1 ,
- CRP (mg/dL) ≤ 1 , and
- patient global assessment ≤ 1 (on a 0-10 scale).

Specifically, let Boolean_28 be defined as follows:

- Boolean_28 = 1,
if a subject fulfills the definition of Boolean remission (28-joint count);
- Boolean_28 = missing,
if any components of the Boolean remission definition are missing;
- Boolean_28 = 0,
otherwise.

Boolean remission (28 joints plus feet/ankles)

A subject achieves Boolean remission (28-joint count plus feet/ankles) if all of the following criteria are met:

- 28-joint plus feet and ankles tender joint count ≤ 1 ,
- 28-joint plus feet and ankles swollen joint count ≤ 1 ,

- CRP (mg/dL) \leq 1, and
- patient global assessment \leq 1 (on a 0-10 scale).

Boolean remission (66/68 joint count)

A subject achieves Boolean remission (66/68-joint count) if all of the following criteria are met:

- 68-joint tender joint count \leq 1,
- 66-joint swollen joint count \leq 1,
- CRP (mg/dL) \leq 1, and
- patient global assessment \leq 1 (on a 0-10 scale).

Let Boolean_68 be defined in a manner similar to that of Boolean_28.

C-Reactive Protein (CRP)

A specific measure of inflammatory activity measured in mg/dL.

Disability Index of the Health Assessment Questionnaire (HAQ-DI)

The HAQ-DI assesses the subject's physical function or disability. The questionnaire asks about the degree of difficulty a person has in accomplishing tasks in 8 functional areas (dressing and grooming, arising, eating, walking, hygiene, reach, grip, and activities). Responses in each functional area are scored from 0 indicating no difficulty to 3 indicating inability to perform a task in that area.

Details of the scoring algorithm are described in [Appendix D](#).

Medical Outcomes Health Survey Short Form 36 Items Version 2 (SF-36 v2)

The SF-36 v2 is a 36-item instrument that measures general health status and will be scored using the QualityMetric Health Outcomes Scoring Software. It includes 8 multi-item scales, each of which assesses one of the following 8 health concepts over the previous month: 1) limitations in physical activities because of health problems; 2) limitations in social activities because of physical or emotional problems; 3) limitations in usual role activities because of physical health problems; 4) bodily pain; 5) general mental health (psychological distress and well-being); 6) limitations in usual role activities because of emotional problems; 7) vitality (energy and fatigue); and 8) general health perceptions. SF-36 v2 includes the Physical Component Summary and Mental Component Summary measures. A higher score represents less disability.

7. Analysis Subsets

